9.6 DATA MANAGEMENT

The data will be extracted through standardized SAS queries that are distributed to health systems and executed against the most recently approved PCORnet CDM. Data will be delivered to [REDACTED] via secure shared Box folders and linked to death data using Datavant Software. All analyses will be performed using SAS v9.4 or R. Only individuals on the IRB for this project will have access to the data, and it will all be stored on secure servers behind the [REDACTED] firewall.

Missing data (e.g., for demographics, vital signs, lab measures) will be documented to report extent of missingness. Missing data will be excluded from denominators in descriptive summaries. For regression models, extent of missing covariate data will be evaluated and appropriate measures for covariates will be taken. This may include multiple imputation or defining the covariate differently, when possible.

For diagnoses, procedures and medications, absence of a relevant code during the specified time window will be interpreted as 'no evidence'. For these factors we hope to avoid possible

misclassification through appropriate eligibility criteria (e.g., restricting to patients with evidence of interaction within the health system). For time-to-event analyses, follow-up will be censored early if patient has lost contact with the health system (defined as 18 months after last encounter with the health system).

9.7 DATA ANALYSIS

Below is an overview of the statistical analyses planned for this project and the approach to implementation of the analyses.

9.7.1 Phased Implementation of Analyses

A phased approach to implementation of data analyses will be used to allow examination of key aspects of the patient populations by treatment group and the prescribing practices by treatment type (i.e., empagliflozin, any SGLT2i, DPP4i and (if feasible) GLP1RA). A first phase of the analyses will focus on descriptive evaluation of differences in demographic and clinical patient characteristics, number and timing of prescriptions across treatment groups, and summary of outcome event rates aggregated across treatment arms. The main rationale for this phased analytic approach is to examine the potential for exposure misclassification due to the limited medication exposure data available in PCORnet (e.g., no pharmacy claims data). Secondary goals of the initial phase will be to assess the degree to which patient characteristics have been well balanced after propensity score weighting, and to confirm that the study will have adequate statistical power based on observed sample size and aggregate event rates for key outcomes. Results from this first analytic phase will be examined and discussed by members of the study team (BI and [REDACTED]) prior to implementation of comparative outcome analysis to provide an opportunity for modification of the study protocol (if needed) and/or study discontinuation if determined appropriate. Additional details for the phased analytic approach, along with codelists and table shells, are provided in the SEAP.

9.7.2 Main analysis

9.7.2.1 Describe the demographic and clinical characteristics of the overall cohort, stratified by DKD status and drug comparator

Analysis: Baseline characteristics will be presented separately for each comparison cohort identified in sections above, resulting in one set of tables for each 2-arm comparison. Characteristics will include demographics, medical history, lab values, and concomitant medications. Continuous variables will be summarized as mean (standard deviation), median [25th percentile, 75th percentile], 5th and 95th percentiles, and minimum, maximum. Categorical variables will be presented as frequencies (%), as will any continuous variable that is further categorized.

Characteristics will be presented in the unweighted cohorts. Additionally, characteristics will be stratified by DKD status and drug comparators. The degree of imbalance in variables

between comparator arms will be quantified with absolute standardized mean differences (see also Objective 2).

9.7.2.2 Generate propensity score models and overlap weights

Analysis: We will use post-LASSO overlap weighting to create the weights for analysis within the DKD and no DKD groups separately. For each two-arm study, propensity score models will be built using a logistic LASSO model with the covariates of interest and all subgroup (see section below) by covariate pairwise interactions. The outcome of interest is treatment group, with empagliflozin [or any SGLT2i] as the treatment group of interest and DPP4i [or GLP1RA] as the reference treatment. In the post-LASSO approach, the variables/interactions that are remaining in the LASSO model are refit to a standard logistic regression to get the final propensity score estimates and weights (effects/probabilities from the LASSO model would have faults due to shrinkage of the coefficient estimates) and the overlap weights. The predicted probabilities from the refit logistic regression are considered the propensity scores. For patients on the reference treatment, the overlap weight is the same as the PS. For patients on the treatment of interest, the overlap weight is 1-PS. No trimming is required due to the PS weights being bounded between 0 and 1.

For each patient, the overlap weight is the predicted propensity that the patient received the treatment opposite from what they were initiated on. For example, for the comparison of empagliflozin versus DPP4i initiation, a patient who was initiated on empagliflozin will receive a weight equal to $(1-ps)$, where 'ps' is the estimated propensity score for empagliflozin initiation, and a patient who was initiated on DPP4i is weighted by 'ps'.

Baseline characteristics will be presented in the reweighted populations. Distributions of covariates in the DKD and no DKD groups and further within subgroups of interest will be assessed using standardized mean differences. Absolute standardized mean differences will be visually depicted using the CONNECT-S plot. Absolute standardized mean differences should be below 0.10 across covariates and subgroups but those that are less than 0.25 might be acceptable.

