
Secondary effectiveness outcomes:
 
 • Individual renal events: 40% decline in eGFR, incident ESRD, dialysis, and kidney transplant • Hospitalizations for cardiovascular events: heart failure (HF), HF+ACD, myocardial infarction+stroke+coronary revascularization+ACD, myocardial infarction+stroke+ACD • ACD 
Secondary safety outcomes:
 
 • Diabetic ketoacidosis • Severe hypoglycaemia • Urinary tract cancer • Acute kidney injury (AKI) that requires dialysis • Genital mycotic infection • Severe urinary tract infections 
Covariates: Several baseline patient characteristics will be captured in the 12 months prior to the index date. Covariates that will be included as covariates in the propensity scores (PS) model include (not are not limited to):
 
 • Demographics (age, sex, race/ethnicity, BMI, quarter and year of incident prescription, smoking status) • Comorbidities: history of heart failure, history of CV events (MI, stroke, PCI, CABG, PAD), hypertension • Prior/concomitant use of other glucose lowering agents • Prior/concomitant use of other medications e.g., cardiovascular agents (ACE/ARB, beta blocker, ARNi, statin) and diuretics • Relevant lab test results, e.g., eGFR, HbA1c, HDL-c, etc. 
Note: See Section 9.3.3 for complete list of covariates
			
Data sources:		This study will utilize high-quality renal function laboratory data available in medical electronic health records from approximately 20	

Name of company: Boehringer Ingelheim			
Name of finished medicinal product: Jardiance®			
Name of active ingredient: A10BK03 Empagliflozin			
Protocol date: 26 May 2023	Study number: 1245-0228	Version/Revision: 2.0	Version/Revision date: 26 May 2023

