
 No observed prescriptions for the index drug within 1 year (+30 days) from the last observed prescription 
The primary analysis will be performed using overlap weighting to balance covariates across the two treatment arms (empagliflozin vs DPP4i) and Cox proportional hazards modelling to determine the effect of drug on outcomes. To create the overlap weights, the following will be performed:
 
For each two-arm study comparison and within the DKD and non-DKD subgroups separately, propensity score models will be built using a logistic LASSO model with the covariates of interest and all subgroup by covariate pairwise interactions. The outcome of interest is treatment group, with empagliflozin [or any SGT2i] as the treatment of interest and DPP4i [or GLP1RA] as the reference group. The variables/interactions that are remaining in the LASSO model are refit to a standard logistic regression and the resulting predicted probability for each patient is considered the PS. For patients on the reference treatment, the overlap weight is the same as the PS. For patients on the treatment of interest, the overlap weight is 1-PS. No trimming is required due to the PS weights being bounded between 0 and 1. Distributions of covariates in the DKD and non- DKD groups and further within subgroups of interest will be assessed using standardized mean differences. Absolute standardized mean differences will be visually depicted using the CONNECT-S plot.
 
For each outcome, incidence rates (number of events per 1000 PY of follow-up), hazard ratios, and corresponding 95% confidence intervals (CI) will be presented. Hazard ratios and CI will be calculated using weighted Cox proportional hazards models. For the AT analysis, if an empagliflozin or DPP4i user initiates a GLP1RA during the follow-up period, this will be adjusted for in the comparison of empagliflozin and DPP4i (and similarly for users initiating a DPP4i).
 
Analyses will be performed overall and within DKD subgroups. A sensitivity analysis will be performed using propensity score
			

Proprietary confidential information © 2023 Boehringer Ingelheim International GmbH or one or more of its affiliated companies

Name of company: Boehringer Ingelheim			
Name of finished medicinal product: Jardiance®			
Name of active ingredient: A10BK03 Empagliflozin			
Protocol date: 26 May 2023	Study number: 1245-0228	Version/Revision: 2.0	Version/Revision date: 26 May 2023

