9.7.2.3 Determine the effect of empagliflozin compared to DPP4i on outcomes

Analysis: The effect of empagliflozin compared to DPP4i on outcomes will be assessed using Cox proportional hazards models in a 2-arm comparison. The analysis will include all patients with a valid overlap weight and will be done for overall and within DKD subgroups. The main analysis will assess outcomes while patients remain on initial treatment.

Follow-up will start the day after the index date (date of initiation of empagliflozin or DPP4i) and will continue until the first occurrence of the outcome of interest, or end of study date (date of death, date of study end, 2 years after index date). For the main AT analysis, follow up will be censored early if an empagliflozin user starts a DPP4i or other type of SGLT2i, or if a DPP4i user starts any SGLT2i. For the AT analysis, if an empagliflozin or DPP4i user initiates a GLP1RA, this will be adjusted for in the model using a time-dependent indicator

variable. Additionally, follow-up will be censored early if there is no indication of a new prescription in the year (+30 days) following the last observed prescription.

Incidence rates will be computed as the number of first events per 100 patient years of follow-up. Analyses of time to first event will be performed using Cox proportional hazards models. Outcomes where death is a competing risk will be analyzed using cause-specific proportional hazards models, achieved by censoring follow-up at the time of death. All analyses will be adjusted for covariates (variables) that continue to be unbalanced after reweighting, with any additional covariates that might be of medical interest identified by the clinicians. Hazard ratios comparing empagliflozin to DPP4i with 95% confidence intervals and the adjusted two-sided p-values for superiority testing will be presented for all outcomes.

Kaplan-Meier curves will be created for each outcome in the overall and DKD subgroups using the reweighted population. Kaplan-Meier curves will also be generated to summarize the cumulative incidence of treatment switching by comparator arm.

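### As worded, the LASSO can drop prespecified confounders, not only interactions, from the propensity model, giving up exact mean balance that overlap weighting would give them

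*Protocol*

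**What the plan says.** Section 9.7.2.2 builds the propensity score separately in the DKD and non-DKD groups, starting from a "logistic LASSO model with the covariates of interest and all subgroup (see section below) by covariate pairwise interactions". The dependent variable is treatment group. After selection, "the variables/interactions that are remaining in the LASSO model are refit to a standard logistic regression"; the Abstract repeats the rule ("The variables/interactions that are remaining in the LASSO model are refit to a standard logistic regression"). The final scores come from that second fit: "The predicted probabilities from the refit logistic regression are considered the propensity scores". The weights follow from them: "For patients on the treatment of interest, the overlap weight is 1-PS", with the score itself as the weight in the reference group.

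The Abstract introduces its list of demographics, comorbidities, medications and laboratory values with "Covariates that will be included as covariates in the propensity scores (PS) model include".

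On what remains after weighting, Section 9.7.2.2 says "Absolute standardized mean differences should be below 0.10 across covariates and subgroups but those that are less than 0.25 might be acceptable", and Section 9.7.2.3 says "All analyses will be adjusted for covariates (variables) that continue to be unbalanced after reweighting". The latter sentence goes on to allow further covariates that clinicians consider medically relevant. Section 9.7.1 makes balance after weighting one of the items reviewed in the first phase, before any comparative outcome analysis.

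**The concern.** The candidate set contains main effects and interactions, and only survivors are refit. The stated rule therefore lets variables be removed as well as interactions, and selection looks only at how well a term predicts treatment. A covariate with a weak link to treatment and a strong link to renal events or death can be discarded, yet it is the kind of variable that one lists in advance in order to control it.

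This sits badly with the Abstract, which says the listed covariates will be in the model. It also gives up a property that makes overlap weighting attractive: with an unpenalised logistic score, the weighted means of every modelled term agree exactly between arms. Because the models are fitted by stratum, a covariate may be kept in one stratum and dropped in the other. Its exact balance is then lost in the second stratum and in the pooled cohort. At stake is avoidable residual confounding in covariates that the study has already decided matter.

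**Working it through.** **1. Why modelled terms balance exactly.** Let T = 1 for the treatment of interest and e be the fitted score, with weights 1 − e when T = 1 and e when T = 0. An unpenalised logistic fit solves, for each term x in the model including the intercept,

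Σ (T − e) x = 0, that is, Σ over T=1 of (1 − e) x = Σ over T=0 of e x.

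The intercept (x = 1) makes the total weights of the two arms equal. Dividing, the weighted mean of x is the same in both arms. A term absent from the refit has no such equation.

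**2. How much is lost when terms are dropped.** The protocol gives neither the number of covariates nor the penalty rule, so these settings are assumptions.

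- *Simulation A:* 34 main effects, 120 interactions, 20 continuous confounders (12 of them weak), 4 subgroup indicators, penalty at 0.03 to 0.30 of its maximum. Total N was 3,000 or 15,200 (2 × the planned 7,600).
  - Across both sizes, the LASSO dropped 10 to 26 of the 34 main effects, including 2 to 12 of the 20 confounders.
  - Terms kept in the refit balanced to about 3e-14 or better.
  - The worst ASMD among dropped main effects was 0.030 to 0.218 at N = 3,000 and 0.012 to 0.070 at N = 15,200.
  - With all main effects forced in, the worst ASMD was zero to machine precision at every penalty.
- *Simulation B:* 40 covariates, 4 subgroups, weak confounders at 0.06 to 0.08 log-odds per SD, cross-validated penalty (minimum and one-standard-error rules).
  - At N = 2,000, 4 to 8 of 16 weak confounders were dropped and the worst ASMD was 0.045 to 0.065.
  - At N = 5,000 the worst ASMD was 0.03 to 0.05.
  - With main effects forced in, it was 0.000.

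**3. From imbalance to bias.** For one covariate with an assumed hazard ratio of 1.5 per SD, the bias factor is approximately exp(ASMD × ln 1.5), with ln 1.5 = 0.4055.

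| ASMD | Shift in log HR | Bias in HR |
|---|---|---|
| 0.012 | 0.0049 | 0.5% |
| 0.030 | 0.0122 | 1.2% |
| 0.065 | 0.0264 | 2.7% |
| 0.070 | 0.0284 | 2.9% |
| 0.10 | 0.0405 | 4.1% |
| 0.218 | 0.0884 | 9.2% |
| 0.25 | 0.1014 | 10.7% |

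**4. Scale against the design.** Section 9.5 gives 7,593 per group in Table 4 for HR 0.80 at 30 per 1,000 patient-years. A log-rank calculation by the Lakatos method (12 subintervals over 24 months, uniform 12-month accrual) returns 7,588, so the plan's figure reproduces. The point itself does not depend on it. The Schoenfeld formula gives 631 events, hence a standard error of the log HR of about 2/√631 = 0.080, ignoring weighting. A shift of 0.0264 is 0.0264/0.080 = 0.33 of a standard error, and 0.0264/0.223 = 12% of the targeted log HR (|ln 0.80| = 0.223).

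**5. Cost of forcing main effects in (simulation A).** At the heaviest cost seen, effective sample size fell from 2,259 to 2,193 at N = 3,000 (66/2,259 = 2.9%) and from 13,298 to 13,195 at N = 15,200 (103/13,298 = 0.8%). At the lightest penalty the fall was about 0.1% or less.

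**The case against.** The best defence is that the plan does not stop at the propensity model. Balance is checked covariate by covariate and within subgroups, the first phase reviews it before any hazard ratio is seen, and the outcome model adjusts for what stays unbalanced. Clinicians may also add covariates whatever their ASMD. A reader might infer that adjustment happens only when an imbalance passes the threshold; the clinician clause in Section 9.7.2.3 rules that out. It is discretionary, however. A gap below 0.10 meets the plan's own target and would not be expected to prompt adjustment, and the range from 0.10 to 0.25 is left to judgement. Nor does adjusting the Cox model correct the Kaplan-Meier curves planned in the reweighted population.

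Second, Section 9.3.3 leaves the covariate list to the SEAP, which is not at hand and may exempt main effects from the penalty. That is fair, and no claim is made about what the SEAP does. But the protocol itself fixes which terms enter the refit, and its wording does not carry the exemption.

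Third, the sizes are small and rest on invented settings. This stands. At 15,200 patients every imbalance was below 0.10, and the 0.218 came from 3,000 patients on an arbitrary penalty grid. Section 9.1 would also drop subgroup analyses if the required sample size is not met.

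Fourth, penalising main effects is not wholly without purpose. Calendar quarter and year over 2015 to 2020 could give up to 6 × 4 = 24 levels, and forcing sparse levels into stratum-specific models may cause instability. This stands too, and the fix allows for it.

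**Conclusion.** The protocol's rule allows prespecified confounders to be removed on treatment prediction alone. This conflicts with the Abstract's statement that they will be in the model, and it forgoes exact weighted mean balance for whatever is removed. This is a cheap improvement, not a flaw that undermines the study.

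At the planned overall size the residual imbalance is probably below 0.10, or about 0.5% to 3% bias in the hazard ratio per covariate. That rests on the simulated covariate structure, the penalties tried and an assumed hazard ratio of 1.5 per SD. Several dropped covariates may add up or cancel. The imbalance could be larger if a DKD or non-DKD stratum is small, since each model sees only its own stratum.

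Two stronger readings are not supported. One is that the DKD cohort or the SGLT2i versus GLP1RA cohort must be the worst affected: the protocol gives no expected size for either. The other is that forcing main effects in is free: it cost up to 2.9% of effective sample size in simulation.

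**What to change.** Amend Section 9.7.2.2, and the matching Abstract text, to say three things:

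- The main effects of all prespecified propensity-score covariates and the subgroup indicators are left unpenalised, or are added back before the refit.
- The LASSO selects only among the subgroup-by-covariate interactions.
- Sparse categorical levels, such as calendar quarter, are collapsed where needed so that the stratum-specific fits are stable.

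If the SEAP already does this, the protocol need only say so. The change takes one or two sentences and a penalty-factor setting, needs no new data, and brings the method into line with the Abstract's covariate statement. The balance check and the outcome-model adjustment stay as they are. The statistical price is the small loss of effective sample size shown above.

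### At stratum and pooled level, overlap weighting sets the standardized mean difference of every retained propensity term to zero, so the balance check cannot reveal a wrong functional form for those terms

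*Protocol*

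**What the plan says.** Protocol section 9.7.2.2 fixes each step of the weighting, separately in the DKD and non-DKD groups:

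- After LASSO selection, "the variables/interactions that are remaining in the LASSO model are refit to a standard logistic regression".
- The scores come from that refit and not from the LASSO: "The predicted probabilities from the refit logistic regression are considered the propensity scores".
- A patient started on the drug under study is weighted by one minus the score, and a patient started on the comparator by the score itself.
- Nobody is trimmed, on the ground that the weights lie between 0 and 1 anyway.

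Balance is then judged as follows: "Distributions of covariates in the DKD and no DKD groups and further within subgroups of interest will be assessed using standardized mean differences". The limit is an absolute SMD below 0.10, with values under 0.25 possibly tolerated.

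Two later steps use the result. Section 9.7.1 makes it part of the Phase 1 review that precedes any outcome comparison: "Secondary goals of the initial phase will be to assess the degree to which patient characteristics have been well balanced after propensity score weighting". Section 9.7.2.3 uses it to choose further adjustment: "All analyses will be adjusted for covariates (variables) that continue to be unbalanced after reweighting". Clinicians may add covariates of medical interest to that adjustment.

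**The concern.** An SMD compares means, and this weighting scheme equates the means of whatever is in the refit. A zero for a retained covariate is therefore a consequence of the fitting algorithm. It says nothing about whether the covariate's relation to treatment choice was given the right shape.

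If age, eGFR, HbA1c or BMI acts non-linearly on both prescribing and outcome and enters the model only linearly, its mean will match perfectly between arms while its spread or tails may not. At stratum and pooled level the balance display would look ideal, the clause on residual imbalance would not be triggered for that covariate, and the remaining confounding would pass into the primary hazard ratio.

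**Working it through.** **1. The identity.** Let Z = 1 for the treatment of interest and Z = 0 for the reference, and let PS be the fitted probability from the refit. Maximum likelihood gives, for each fitted term x,

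Σ (Z − PS) x = 0.

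Since Z − PS = Z(1 − PS) − (1 − Z)PS, this is the same as

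Σ over treated of (1 − PS) x = Σ over reference of PS x.

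The factors are exactly the overlap weights in section 9.7.2.2. Putting x = 1 (the intercept) shows that the two weight totals are equal. The weighted means of x are therefore equal and the SMD is 0. The true assignment model does not enter. With no trimming, the weighted sample is the fitting sample. The equal sums add across the two strata, so the result carries over to the pooled cohort for any term kept in both.

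**2. Numerical check of the identity.** Cohorts of 15,200 were simulated (2 × 7,600, the section 9.5 size), with penalised selection over six covariates, a subgroup and all subgroup-by-covariate terms, then an unpenalised refit. Assumed assignment models were correct or misspecified.

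| Quantity | Result |
|---|---|
| Largest SMD of retained terms, all four runs | at most 1.2e-16 |
| SMD of the covariate's square, misspecified model | 0.56 |
| SMD of the covariate's square, correct model | 0.033 |
| Retained terms, LASSO probabilities without refit | 0.007 to 0.105 |
| Retained terms, inverse-probability weights, misspecified refit | about 0.16 |

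The exact zero comes from combining the refit with overlap weights. The other two constructions do not give it.

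**3. Where the check can still fail.** With a covariate and a subgroup indicator kept as main effects but their interaction left out, the covariate's SMD was 0 in the full stratum, 0.19 in one subgroup and 0.52 in the other. Adding the interaction brought both to 0.

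**4. Possible size of bias.** Inputs from section 9.5: 15,200 patients and 1.5 years of follow-up. Assumed: about 27 events per 1,000 patient-years at covariate means (the design rate is 30), a true hazard ratio of 1.0, a propensity model linear in two covariates, and a quadratic term in one of them with opposite signs in assignment and log hazard. The estimate was a weighted rate ratio with approximate variance, not the planned weighted Cox model. With assumed linear coefficients of 0.4 and 0.3 in both models and 300 replicates:

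| Quadratic coefficients (assignment / log hazard) | Largest SMD, modelled terms | Absolute SMD of square | Mean HR | False rejection |
|---|---|---|---|---|
| −0.05 / +0.05 | 1e-16 | 0.06 | 0.99 | 5% |
| −0.10 / +0.10 | 1e-16 | 0.12 | 0.96 | 7% |
| −0.15 / +0.15 | 2e-16 | 0.18 | 0.91 | 23% |
| −0.20 / +0.20 | 1e-16 | 0.24 | 0.87 | 48% |

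Two similar simulations gave:

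- HR 0.91 (24% false rejection) at 0.15, and 0.85 (49%) at 0.20.
- With weaker hazard effects (linear coefficients 0.3 and 0.2), HR 0.94 (12%) at 0.15 and 0.88 (44%) at 0.20. Coefficients of 0.03 to 0.05 gave 0.99 to 1.00, with 3.5% to 4.5% rejection.

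To read the scale, take a standardised covariate at 2 standard deviations from its mean. A coefficient of 0.15 adds 0.15 × 4 = 0.60 to the log hazard, a factor of exp(0.60) = 1.82. A coefficient of 0.05 adds 0.20, a factor of 1.22. The larger scenarios therefore assume strong curvature.

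**5. Does the remedy work?** A limit of 0.10 on the square leaves the harmless scenario alone (0.06) and flags the other three (0.12, 0.18, 0.24). Adding the square to the refit restored HR 1.00 with 3% rejection in the two larger scenarios. An omitted product term reached an SMD of 0.27, yet the HR stayed at 0.98 to 1.01, so squares matter more than products here.

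**The case against.** Exact mean balance is what overlap weighting is designed to deliver, and nothing in the weights or the refit is wrong. That stands. A reader might infer an error in the weighting, and the protocol does not support that.

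A reader might also infer that the balance check is empty, or that every modelled covariate passes it everywhere. That goes too far. Section 9.7.2.2 applies the limits across covariates and subgroups, so dropped terms are already in scope, and a retained covariate can fail inside a subgroup whose interaction was not kept. Section 9.3.3 refers to baseline variables that stay outside the propensity model. Section 9.7.2.3 lets clinicians add covariates. The propensity-matching sensitivity analysis in the abstract is not subject to the identity.

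Nor does the protocol say that a small SMD proves the model right. It speaks of balance only. It also does not say that continuous covariates enter linearly; the covariate list is left to the analysis plan, which is not shown and may use splines. Section 9.7.2.1 allows continuous variables to be categorised as well, and SMDs of categories of a linearly modelled variable are not forced to zero.

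These points limit the concern but do not remove it. Section 9.7.2.2 sets out to assess distributions, yet the only metric it names compares means, and for retained terms at stratum and pooled level that metric has only one possible value.

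**Conclusion.** The point holds as a cheap improvement. For terms kept in the refit, the SMD in the fitting stratum and in the pooled cohort is zero by algebra. At that level the 0.10/0.25 rule, the Phase 1 review and the residual-imbalance clause carry no information about functional form. Exactness needs a converged unpenalised fit with an intercept on the same patients. Under multiple imputation, which section 9.6 allows, it holds within each completed dataset but not necessarily with averaged scores.

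A reader might infer that the primary hazard ratio will be biased by a known amount. The documents give no curvature, so no size can be fixed. Bias is negligible if curvature is mild (HR 0.99 to 1.00), about 0.96 at coefficients of 0.10, and 0.85 to 0.94 only under assumed strong curvature of opposite sign in assignment and hazard. Against the design hazard ratio of 0.80, that last range is ln(0.94)/ln(0.80) = 28% to ln(0.85)/ln(0.80) = 73% of the planned log effect. That justifies an inexpensive safeguard.

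**What to change.** In section 9.7.2.2:

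1. State that stratum-level and pooled SMDs of retained terms are zero by construction and are not evidence that the propensity model is adequate.
2. Add to the Phase 1 balance tables the weighted SMDs of the squared continuous confounders (age, eGFR, HbA1c, BMI) and their weighted variance ratios.
3. Where a squared term exceeds 0.10, add it or a spline to the propensity refit before any outcome comparison.

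If the analysis plan already does this, a cross-reference is enough. Section 5 shows that some Phase 1 results were in hand when version 2.0 was written, so the new rows may have to supplement existing tables. What matters is that they come before the comparative analysis.

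The cost is a few sentences and some extra table rows from variables already collected. The downside is a few more propensity terms and slightly less overlap.
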